4.7 Safety Endpoints

The evaluation of drug safety is based on clinical adverse events and laboratory abnormalities reported during the study. All safety presentations will be based on actually-treated subject dataset.

AEs and SAEs will be summarised using the following method:

Number and percentage of subjects who ever reported adverse event (AE) and serious adverse event (SAE) together with the number of AEs and SAEs will be presented by treatment group. The severity and outcome of AEs and SAEs, relationship to treatment and action taken will be summarised.

Same AE term reported at multiple level of severities by a single subject will be counted for each level of severity, not just the highest severity. Under subject counts at each severity category, only unique subject will be counted. The same method will also be applied for summaries by relationship, treatment given, outcome, and action taken.

All on-study adverse events will be further summarised by MedDRA terminology. Summaries of AEs will be based on the resulting system organ class (SOC) and preferred terms (PT). All reported SAEs will be listed indicating the subject ID, SAE criteria, randomisation date, onset date, resolution date, relationship to study treatment and outcome of causality.

The term “AEs” used in the summaries would cover severe AEs and SAEs as well.

Number of subjects who ever experienced the following medical events including acute myocardial infarct, ischaemic stroke, new cancer (non-colorectal), major GI bleeding (requiring blood transfusion), haemorrhagic stroke and major nervous system bleeding throughout the study will be counted and its corresponding percentages will be respectively compared between the two treatment groups using Fisher’s exact test.

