7.8. Anticipated side effects of Aspirin

Side effects that occasionally occur are gastrointestinal disorders such as nausea, vomiting, diarrhoea, and slight gastrointestinal blood loss which in exceptional cases can lead to anaemia. Gastrointestinal ulcers may rarely develop, in some circumstances with haemorrhaging and

perforation. Dizziness and ringing in the ear can occur as symptoms of over dosage, especially in children and elderly patients.

Rare cases of hypersensitivity reactions (e.g. difficulty in breathing, skin reaction) can occur.

Isolated cases of liver and kidney function disturbances, and severe skin reactions have been reported.

The absolute annual increase risk attributable to Aspirin for major bleeding, major gastrointestinal bleeding and intracranial haemorrhage is estimated at 0.13%, 0.12% and 0.03% respectively. (McQuaid KR et al)

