Appendix 1: Mock-up tables

Table 1: Subject status and demographics

	Modified intention-to-treat			Per-protocol		
	Aspirin	Placebo	Total	Aspirin	Placebo	Total
Number of subjects randomised	xxx	xxx	xxx	xxx	xxx	xxx
Number of subjects ineligible but randomised, n (%)	xx (xx.x)	xx (xx.x)	xx (xx.x)	xx (xx.x)	xx (xx.x)	xx (xx.x)
Subjects discontinued study treatment, n (%)	xx (xx.x)	xx (xx.x)	xx (xx.x)	xx (xx.x)	xx (xx.x)	xx (xx.x)
Completed protocol treatment	xx (xx.x)	xx (xx.x)	xx (xx.x)	xx (xx.x)	xx (xx.x)	xx (xx.x)
AE/SAE	xx (xx.x)	xx (xx.x)	xx (xx.x)	xx (xx.x)	xx (xx.x)	xx (xx.x)
Protocol violation/ ineligibility	xx (xx.x)	xx (xx.x)	xx (xx.x)	xx (xx.x)	xx (xx.x)	xx (xx.x)
Clinical decision	xx (xx.x)	xx (xx.x)	xx (xx.x)	xx (xx.x)	xx (xx.x)	xx (xx.x)
Subject decision	xx (xx.x)	xx (xx.x)	xx (xx.x)	xx (xx.x)	xx (xx.x)	xx (xx.x)
Recurrence	xx (xx.x)	xx (xx.x)	xx (xx.x)	xx (xx.x)	xx (xx.x)	xx (xx.x)
Death	xx (xx.x)	xx (xx.x)	xx (xx.x)	xx (xx.x)	xx (xx.x)	xx (xx.x)
Others	xx (xx.x)	xx (xx.x)	xx (xx.x)	xx (xx.x)	xx (xx.x)	xx (xx.x)
Subjects who did not complete study, n (%)	xxx (xx.x)	xxx (xx.x)	xxx (xx.x)	xxx (xx.x)	xxx (xx.x)	xxx (xx.x)
Subject withdrew consent	xx (xx.x)	xx (xx.x)	xx (xx.x)	xx (xx.x)	xx (xx.x)	xx (xx.x)
Withdrawn from study by investigator	xx (xx.x)	xx (xx.x)	xx (xx.x)	xx (xx.x)	xx (xx.x)	xx (xx.x)
Lost to follow-up	xx (xx.x)	xx (xx.x)	xx (xx.x)	xx (xx.x)	xx (xx.x)	xx (xx.x)
Death	xx (xx.x)	xx (xx.x)	xx (xx.x)	xx (xx.x)	xx (xx.x)	xx (xx.x)
Others	xx (xx.x)	xx (xx.x)	xx (xx.x)	xx (xx.x)	xx (xx.x)	xx (xx.x)

Subject follow-up completion, n (%)

1 year follow-up	XX (XX.X)	XX (XX.X)	XX (XX.X)	XX (XX.X)	XX (XX.X)	XX (XX.X)
2 year follow-up	XX (XX.X)	XX (XX.X)	XX (XX.X)	XX (XX.X)	XX (XX.X)	XX (XX.X)
3 year follow-up	XX (XX.X)	XX (XX.X)	XX (XX.X)	XX (XX.X)	XX (XX.X)	XX (XX.X)
4 year follow-up	XX (XX.X)	XX (XX.X)	XX (XX.X)	XX (XX.X)	XX (XX.X)	XX (XX.X)
5 year follow-up	XX (XX.X)	XX (XX.X)	XX (XX.X)	XX (XX.X)	XX (XX.X)	XX (XX.X)

Subject follow-up time, month

Mean (SD)	XX.X (XX.X)	XX.X (XX.X)	XX.X (XX.X)	XX.X (XX.X)	XX.X (XX.X)	XX.X (XX.X)
Median (IQR)	XX.X (XX.X)	XX.X (XX.X)	XX.X (XX.X)	XX.X (XX.X)	XX.X (XX.X)	XX.X (XX.X)
Min, Max	XX.X, XX.X	XX.X, XX.X	XX.X, XX.X	XX.X, XX.X	XX.X, XX.X	XX.X, XX.X

Demographics

Age, year

n	XXX	XXX	XXX	XXX	XXX	XXX
Mean (SD)	XX.X (XX.X)	XX.X (XX.X)	XX.X (XX.X)	XX.X (XX.X)	XX.X (XX.X)	XX.X (XX.X)
Median (IQR)	XX.X (XX.X)	XX.X (XX.X)	XX.X (XX.X)	XX.X (XX.X)	XX.X (XX.X)	XX.X (XX.X)

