Past history	xxx (xx.x)	xxx (xx.x)	xxx (xx.x)	xxx (xx.x)
No	xxx (xx.x)	xxx (xx.x)	xxx (xx.x)	xxx (xx.x)
Unknown	xxx (xx.x)	xxx (xx.x)	xxx (xx.x)	xxx (xx.x)
Other cancers, n (%)				

Current active	xxx (xx.x)	xxx (xx.x)	xxx (xx.x)	xxx (xx.x)
Past history	xxx (xx.x)	xxx (xx.x)	xxx (xx.x)	xxx (xx.x)
No	xxx (xx.x)	xxx (xx.x)	xxx (xx.x)	xxx (xx.x)
Unknown	xxx (xx.x)	xxx (xx.x)	xxx (xx.x)	xxx (xx.x)
ECOG at screening, n (%)				
0: Asymptomatic	xxx (xx.x)	xxx (xx.x)	xxx (xx.x)	xxx (xx.x)
1: Symptomatic but completely ambulatory	xxx (xx.x)	xxx (xx.x)	xxx (xx.x)	xxx (xx.x)
2: <50% in bed during the day	xxx (xx.x)	xxx (xx.x)	xxx (xx.x)	xxx (xx.x)
3: >50% in bed, but not bedbound	xxx (xx.x)	xxx (xx.x)	xxx (xx.x)	xxx (xx.x)
4: Bedbound	xxx (xx.x)	xxx (xx.x)	xxx (xx.x)	xxx (xx.x)
Family history				
Number of family members with colorectal cancer (1 st and 2 nd degree relatives only), n (%)				
Nil	xxx (xx.x)	xxx (xx.x)	xxx (xx.x)	xxx (xx.x)
One	xxx (xx.x)	xxx (xx.x)	xxx (xx.x)	xxx (xx.x)
Two	xxx (xx.x)	xxx (xx.x)	xxx (xx.x)	xxx (xx.x)
Three	xxx (xx.x)	xxx (xx.x)	xxx (xx.x)	xxx (xx.x)
≥ Four	xxx (xx.x)	xxx (xx.x)	xxx (xx.x)	xxx (xx.x)
Vital signs at screening				
Weight, kg				
n	xxx	xxx	xxx	xxx
Mean (SD)	xx.x (xx.x)	xx.x (xx.x)	xx.x (xx.x)	xx.x (xx.x)
Median (IQR)	xx.x (xx.x)	xx.x (xx.x)	xx.x (xx.x)	xx.x (xx.x)
Min, Max	xx.x, xx.x	xx.x, xx.x	xx.x, xx.x	xx.x, xx.x

Height, cm					
n	XXX	XXX	XXX	XXX	XXX
Mean (SD)	XX.X (XX.X)	XX.X (XX.X)	XX.X (XX.X)	XX.X (XX.X)	XX.X (XX.X)
Median (IQR)	XX.X (XX.X)	XX.X (XX.X)	XX.X (XX.X)	XX.X (XX.X)	XX.X (XX.X)
Min, Max	XX.X, XX.X	XX.X, XX.X	XX.X, XX.X	XX.X, XX.X	XX.X, XX.X
Systolic blood pressure, mmHg					
n	XXX	XXX	XXX	XXX	XXX
Mean (SD)	XX.X (XX.X)	XX.X (XX.X)	XX.X (XX.X)	XX.X (XX.X)	XX.X (XX.X)
Median (IQR)	XX.X (XX.X)	XX.X (XX.X)	XX.X (XX.X)	XX.X (XX.X)	XX.X (XX.X)
Min, Max	XX.X, XX.X	XX.X, XX.X	XX.X, XX.X	XX.X, XX.X	XX.X, XX.X
Diastolic blood pressure, mmHg					
n	XXX	XXX	XXX	XXX	XXX
Mean (SD)	XX.X (XX.X)	XX.X (XX.X)	XX.X (XX.X)	XX.X (XX.X)	XX.X (XX.X)
Median (IQR)	XX.X (XX.X)	XX.X (XX.X)	XX.X (XX.X)	XX.X (XX.X)	XX.X (XX.X)
Min, Max	XX.X, XX.X	XX.X, XX.X	XX.X, XX.X	XX.X, XX.X	XX.X, XX.X

n: number of subjects; %: percentage of respective population pool treatment group; SD: standard deviation; IQR: interquartile range.

Table 6: Laboratory investigations at screening

	Modified intention-to-treat		Per-protocol	
	Aspirin (N=xxxx)	Placebo (N=xxxx)	Aspirin (N=xxxx)	Placebo (N=xxxx)
Haematology				
Haemoglobin, g/dL				

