Country Y vs. Reference Country	xx.x (xx.x-xx.x)	0.xxx	xx.x (xx.x-xx.x)	0.xxx

Tumour type					
Rectal cancer vs. Dukes C colon cancer			0.xxx		0.xxx
High risk Dukes B colon cancer vs. Dukes C colon cancer	xx.x (xx.x-xx.x)		0.xxx	xx.x (xx.x-xx.x)	0.xxx
Adjuvant chemotherapy (exposed vs. not exposed to Oxaliplatin)	xx.x (xx.x-xx.x)		0.xxx	xx.x (xx.x-xx.x)	0.xxx

Note: Adjusted hazard ratio was estimated using Cox proportional hazard model with trial stratification factors (centre pooled by country (categorical), type of tumour (categorical) and type of adjuvant chemotherapy (categorical)) as covariates.

Table 9: Summary of adverse events

Population: Safety population

	Number of Subjects		Number of Events	
	Aspirin (N=xxxx)	Placebo (N=xxxx)	Aspirin	Placebo
Subjects ever experienced any AE, n (%)	xxx (xx.x)	xxx (xx.x)	xxx	xxx
Severity, n (%)				
Mild	xxx (xx.x)	xxx (xx.x)	xxx	xxx
Moderate	xxx (xx.x)	xxx (xx.x)	xxx	xxx
Severe	xxx (xx.x)	xxx (xx.x)	xxx	xxx
Unknown	xxx (xx.x)	xxx (xx.x)	xxx	xxx
Treatment related, n (%)				
Not related	xxx (xx.x)	xxx (xx.x)	xxx	xxx
Unlikely related	xxx (xx.x)	xxx (xx.x)	xxx	xxx
Possibly related	xxx (xx.x)	xxx (xx.x)	xxx	xxx
Probably related	xxx (xx.x)	xxx (xx.x)	xxx	xxx
Definitely related	xxx (xx.x)	xxx (xx.x)	xxx	xxx
Unknown	xxx (xx.x)	xxx (xx.x)	xxx	xxx
Treatment given, n (%)				
Yes	xxx (xx.x)	xxx (xx.x)	xxx	xxx
No	xxx (xx.x)	xxx (xx.x)	xxx	xxx
Outcome, n (%)				
Recovered	xxx (xx.x)	xxx (xx.x)	xxx	xxx
Recovered with sequelae	xxx (xx.x)	xxx (xx.x)	xxx	xxx
Ongoing	xxx (xx.x)	xxx (xx.x)	xxx	xxx
Death	xxx (xx.x)	xxx (xx.x)	xxx	xxx
Unknown	xxx (xx.x)	xxx (xx.x)	xxx	xxx
Action taken to study treatment, n (%)				
None	xxx (xx.x)	xxx (xx.x)	xxx	xxx
Modified	xxx (xx.x)	xxx (xx.x)	xxx	xxx
Temporarily interrupted	xxx (xx.x)	xxx (xx.x)	xxx	xxx
Permanently discontinued	xxx (xx.x)	xxx (xx.x)	xxx	xxx
Unknown	xxx (xx.x)	xxx (xx.x)	xxx	xxx

AE: adverse event.

Note: Under number of events, the same AE term of multiple severities, relationships, treatments, actions reported by a single subject will be counted separately. Under number of subjects, only unique subjects will be counted.

Table 10: Summary of serious adverse events

Population: Safety population

	Number of Subjects		Number of Events	
	Aspirin (N=xxxx)	Placebo (N=xxxx)	Aspirin	Placebo
Subjects ever experienced any SAE, n (%)	xxx (xx.x)	xxx (xx.x)	xxx	xxx
SAE criteria, n (%)				
Death	xxx (xx.x)	xxx (xx.x)	xxx	xxx
Life-threatening	xxx (xx.x)	xxx (xx.x)	xxx	xxx

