Inpatient hospitalization	xxx (xx.x)	xxx (xx.x)	xxx	xxx
Hospitalization prolonged	xxx (xx.x)	xxx (xx.x)	xxx	xxx
Disability / incapacity	xxx (xx.x)	xxx (xx.x)	xxx	xxx
Congenital anomaly	xxx (xx.x)	xxx (xx.x)	xxx	xxx
Others	xxx (xx.x)	xxx (xx.x)	xxx	xxx
Action taken, n (%)				
None	xxx (xx.x)	xxx (xx.x)	xxx	xxx
Modified to 100mg OD	xxx (xx.x)	xxx (xx.x)	xxx	xxx
Temporarily interrupted	xxx (xx.x)	xxx (xx.x)	xxx	xxx
Permanently discontinued	xxx (xx.x)	xxx (xx.x)	xxx	xxx
Unknown	xxx (xx.x)	xxx (xx.x)	xxx	xxx
Treatment related, n (%)				
Not related	xxx (xx.x)	xxx (xx.x)	xxx	xxx
Unlikely related	xxx (xx.x)	xxx (xx.x)	xxx	xxx
Possibly related	xxx (xx.x)	xxx (xx.x)	xxx	xxx
Probably related	xxx (xx.x)	xxx (xx.x)	xxx	xxx
Definitely related	xxx (xx.x)	xxx (xx.x)	xxx	xxx
Unknown	xxx (xx.x)	xxx (xx.x)	xxx	xxx
Outcome, n (%)				
Recovered	xxx (xx.x)	xxx (xx.x)	xxx	xxx
Recovered with sequelae	xxx (xx.x)	xxx (xx.x)	xxx	xxx
Ongoing	xxx (xx.x)	xxx (xx.x)	xxx	xxx
Death	xxx (xx.x)	xxx (xx.x)	xxx	xxx
Unknown	xxx (xx.x)	xxx (xx.x)	xxx	xxx
Withdrawn due to SAE, n (%)				
Yes	xxx (xx.x)	xxx (xx.x)	xxx	xxx
No	xxx (xx.x)	xxx (xx.x)	xxx	xxx
Causality, n (%)				
Study treatment	xxx (xx.x)	xxx (xx.x)	xxx	xxx

Disease under study	xxx (xx.x)	xxx (xx.x)	xxx	xxx
Other illness	xxx (xx.x)	xxx (xx.x)	xxx	xxx
Concurrent medication / treatment	xxx (xx.x)	xxx (xx.x)	xxx	xxx
Others	xxx (xx.x)	xxx (xx.x)	xxx	xxx
Unknown	xxx (xx.x)	xxx (xx.x)	xxx	xxx

SAE: serious adverse event.

Note: Under number of events, the same SAE term of multiple SAE criteria, actions, relationships, outcomes and causalities reported by a single subject will be counted separately. Under number of subjects, only unique subjects will be counted.

Table 11: Adverse events by system organ class and severity grade

Population: Safety population

System Organ Class Preferred Term	MILD			MODERATE			SEVERE			UNKNOWN		
	n (%)	nAE	n (%)	n (%)	nAE	n (%)	n (%)	nAE	n (%)	n (%)	nAE	n (%)
Aspirin (N = xxx)												
System organ class 1	xx (xx.x)	xx	xx (xx.x)	xx	xx	xx (xx.x)	xx	xx	xx (xx.x)	xx	xx	xx (xx.x)
Preferred term 1	xx (xx.x)	xx	xx (xx.x)	xx	xx	xx (xx.x)	xx	xx	xx (xx.x)	xx	xx	xx (xx.x)
Preferred term 2	xx (xx.x)	xx	xx (xx.x)	xx	xx	xx (xx.x)	xx	xx	xx (xx.x)	xx	xx	xx (xx.x)
Preferred term 3	xx (xx.x)	xx	xx (xx.x)	xx	xx	xx (xx.x)	xx	xx	xx (xx.x)	xx	xx	xx (xx.x)
...	xx (xx.x)	xx	xx (xx.x)	xx	xx	xx (xx.x)	xx	xx	xx (xx.x)	xx	xx	xx (xx.x)
System organ class X	xx (xx.x)	xx	xx (xx.x)	xx	xx	xx (xx.x)	xx	xx	xx (xx.x)	xx	xx	xx (xx.x)

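### SAP 4.7 rests safety partly on laboratory abnormalities, but no planned output shows by arm the haemoglobin scheduled on treatment

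*SAP*

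**What the plan says.** SAP 4.7 opens with "The evaluation of drug safety is based on clinical adverse events and laboratory abnormalities reported during the study". It then gives methods for AEs, SAEs and a list of medical events. It gives no method specific to laboratory values.

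The laboratory data that could serve this purpose are defined elsewhere:

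- Protocol 11.2 takes a baseline Hb within 8 weeks before randomisation. Protocol 11.3 and Appendix 3 repeat Hb at months 6, 12, 18, 24, 30 and 36.
- Protocol 11.3 and SAP 3.4 no longer require Hb once study drug is discontinued or the cancer has recurred. It is therefore in effect an on-drug measurement.
- Protocol 7.8 lists among aspirin's occasional effects "slight gastrointestinal blood loss which in exceptional cases can lead to anaemia".
- Protocol 9.2 includes an asymptomatic Hb drop of more than 2 g/dL from baseline among the events for which it suggests stopping drug, starting a PPI and performing endoscopy. The section is offered as guidance and leaves the decision to the investigator.

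The laboratory table in SAP Appendix 1 is "Table 6: Laboratory investigations at screening", laid out for the mITT and per-protocol sets. The outputs that could carry an Hb fall indirectly are "Table 9: Summary of adverse events", "Table 11: Adverse events by system organ class and severity grade", the Table 1 rows under "Subjects discontinued study treatment, n", and the Table 14 count of major gastrointestinal bleeds, which SAP 4.7 limits to those needing transfusion.

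**The concern.** The SAP names two bases for its safety evaluation but plans outputs for only one. Scheduled Hb is the more even-handed source on blood loss: while patients stay on drug, it is measured on the same timetable in both arms and can be judged against a fixed threshold that the protocol already supplies. AE reporting depends on whether each investigator thinks a fall worth recording.

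What is at stake is the trial's description of tolerability. Protocol 1.8 justifies the 200 mg dose as a balance of efficacy against tolerability. Blood loss that falls short of transfusion belongs in that balance, and it is the kind of effect most likely to go unrecorded or to be recorded unevenly. If the table is specified only after unblinding, the choice of threshold and denominator will be open to the charge that it was made with the results in view.

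**Working it through.** The plan gives no figure to reproduce. The check is an inventory of the planned outputs against the Hb schedule, followed by one count for scale.

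**Step 1. Planned outputs.** Sources: the SAP's lists of tables, figures and listings, and the mock-ups in Appendices 1 and 2.

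| Output | Content | On-treatment Hb by arm? |
|---|---|---|
| Tables 1–5 | Status and demographics, exposure, tumour and adjuvant therapy, risk factors, history and vital signs | No |
| Table 6 | Laboratory values, including Hb, at screening | No (screening only) |
| Tables 7–8 | DFS, OS and Cox models | No |
| Tables 9–13 | AEs and SAEs | Only if reported as an AE |
| Table 14 | Six medical events | No Hb item |
| Figures 1–7 | CONSORT, Kaplan–Meier, forest and cumulative incidence plots | No |
| Listings 1–3 | Protocol deviations and SAEs | No by-arm summary |

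One of the 24 outputs (14 + 7 + 3) contains Hb as a measurement, and none contains on-treatment Hb. The mock-ups after Figure 5 are not visible, but the titles of Figures 6–7 and Listings 1–3 are listed and none concerns laboratory data.

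**Step 2. Text on laboratory summaries.** SAP 4.5 covers laboratory investigations as baseline characteristics. SAP 4.1 gives general descriptive methods. Neither calls for a post-baseline Hb summary.

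**Step 3. Routes by which an Hb fall could still appear by arm.**

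- Reported as an AE: protocol 13.1 allows an abnormal laboratory finding to be an AE. It would then enter Table 9 (with action taken) and Table 11 (by preferred term).
- Leading to discontinuation: it would add to the AE/SAE reason in Table 1, without being identified as an Hb fall.
- Accompanying a transfused gastrointestinal bleed: the bleed, though not the Hb value, would be counted in Table 14.

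The first two routes depend on the investigator's reporting or decision. The third is confined to the most severe bleeds.

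**Step 4. Scale.** Planned number randomised: 1587 (SAP 3.2 Treatment Schedule). Scheduled on-treatment Hb visits: 6 (protocol 11.3).

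1587 × 6 = 9,522 scheduled values.

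This is an upper bound, because Hb is not required after drug discontinuation or recurrence, and deaths and missed visits reduce it further. It says how much data lacks a summary. It does not measure any harm that would be missed.

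**The case against.** The strongest reply is that the sentence in SAP 4.7 may already be met. It speaks of abnormalities that are reported. Protocol 13.1 admits laboratory findings as AEs and asks for all AEs to be recorded, and protocol 9.2 treats the 2 g/dL drop as an event alongside haematemesis and melaena. On that reading, a material fall would be entered as an AE and would appear by arm in Tables 9 and 11, with any stopping of drug in Table 1. SAP 4.1 also supplies general summary methods, so what is missing is a table and a threshold rather than a statistical method. This much stands: it narrows the gap and is why the point is minor. It does not close the gap, because these outputs show what investigators chose to report and none summarises the scheduled measurements.

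A second reply is that the proposed table would itself be weak. Patients who stop drug after a bleed leave the Hb schedule, so the comparison can be biased towards no difference and might falsely reassure. That also stands. It is a reason to report who has no on-treatment Hb and to state the limitation beside the table.

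A reader might infer more than the documents support:

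- *That the SAP breaches its own sentence.* The reading just given prevents that conclusion.
- *That the Hb data are collected for nothing.* They serve the monitoring of individual patients under protocol 9.2. They are simply not tabulated by arm.
- *That the rarity of major bleeds in Table 14, and the low power to compare them, measures the gap.* That describes a different output, and an Hb table would not change it.
- *That phone contact under protocol 11.3 removes Hb visits.* No rule waives Hb at a phone visit, off-site investigations are allowed, and the documents do not say how often phone visits occur.
- *That the DMC did not see Hb.* The listed contents of its safety report in protocol 12.3 do not name Hb, but they do not exclude it.

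**Conclusion.** The point holds as a minor gap in reporting. Followed as written, the planned outputs yield no by-arm result for Hb scheduled at months 6 to 36, although the SAP names laboratory abnormalities as a basis of safety and the protocol both expects blood loss and supplies a threshold for it.

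The conclusion rests on a complete list of outputs and needs no numerical assumption. How much the missing table would show cannot be judged from the documents: they give neither the expected frequency of drops above 2 g/dL nor the proportion of such drops that investigators would report as AEs. Nothing here touches DFS, OS, power, sample size or the type I error rate.

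**What to change.** Before unblinding, add to SAP 4.7 one descriptive table by arm, in the safety population defined in SAP 4.2, giving:

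- (a) the number and percentage of patients with an on-treatment Hb drop of more than 2 g/dL from baseline, among those with a baseline and at least one on-treatment Hb;
- (b) the number of patients with no on-treatment Hb, and why;
- (c) Hb by scheduled visit, with the number measured at each.

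Define the on-treatment window in the text. First dose to 30 days after last dose would match the end of AE recording in protocol 13.2. No significance test is needed.

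State beneath the table that it may understate aspirin harm because Hb is not required after drug discontinuation or recurrence, and that it should be read beside the discontinuations in Table 1 and the AEs in Tables 9 and 11.

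The cost is one extra table from data already collected. The downside is that the comparison may be biased towards no difference, which is why (b) and the caveat should accompany it. No change to visits, data collection or the efficacy analysis is needed.

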9. TREATMENT SCHEDULE

9.1. Treatment groups

The study drug, oral Aspirin 200 mg/ placebo 200 mg OD should be started immediately but no later than 2 weeks after randomisation/baseline visit. The patient will be treated with the same study drug for 3 years.

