9.3. Treatment discontinuation

The investigator has the right to discontinue study treatment if he/she feels that it is in the best interests of the patient or due to safety concerns.

Study drug will be stopped immediately if there is disease recurrence confirmed by CT, histology or cytology, and in the event of an SAE unequivocally related to study drug (or at the discretion of the investigator if the relationship of SAE to the study drug cannot be established with certainty at the time of reporting).

The reasons for treatment discontinuation will be documented. Patients with their treatment discontinued will continue to be followed up until 5 years after randomisation.

Even if a patient chooses not to adhere to the treatment assignment or data collection schedule, every effort should be made to follow patient for the protocol objectives until the end of the study.

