13.2 Reporting of Adverse Event

All AEs will be recorded on the AE form in the subject's case report form.

The site investigator (international site or local site) is responsible to report **all SAEs** with de-identified relevant reports **within 1 working day** of the knowledge of the event to all of the following:

- Attention to monitor or project coordinator
- Investigational Product Manufacturer (Bayer AG)

The site investigator is also responsible to report all SAEs to relevant ethics committee or institutional review board within the required timeline. All SAEs will be followed up until resolution with updated information reported whenever available to the relevant parties as per initial reporting procedure.

The study monitor/project coordinator will notify the study co-chair and study project manager with the submitted SAE report by the site. The study co-chair will review the SAE report and recommendations will be sent to the site investigators if any.

The study co-chair is responsible to ensure any serious and unexpected adverse drug reaction occurring in the study is notified to all participant sites for reporting to ethics committee(s) or institutional review board(s) of all study centres and regulatory body (ies) of the country (ies) where the study is conducted by using the CIOMS Form. Fatal or life-threatening unexpected adverse drug reaction must be notified immediately but no later than 7 calendar days after the first knowledge by the study co-chair, followed by a complete report within 8 additional calendar days. All other serious, unexpected adverse drug reactions that are not fatal or life threatening must be reported within 15 calendar days after first knowledge by the study co-chair. The CIOMS Form will be sent to Bayer AG for review before distributing to all participating sites.

After discontinuation of treatment, patients should be carefully monitored for the occurrence of new adverse events up to 30 calendar days (follow-up period) after the administration of the last dose of aspirin. Adverse events are to be assessed in terms of their seriousness, severity, and relationship to the study drug. Only serious adverse (SAEs) should be reported to Bayer AG.

AEs and SAEs will be recorded from the time of entry into the study until 30 days after the full completion of study treatment, or in instances of early drug termination 30 days after the final cessation of study drug.

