2 STUDY OBJECTIVES

Primary objective

Null hypothesis: Among subjects with Dukes C or high risk Dukes B colorectal cancer, Disease Free Survival (DFS) between those randomised to Aspirin and those randomised to placebo control is equal.

Alternative hypothesis: Among subjects with Dukes C or high risk Dukes B colorectal cancer, DFS between those randomised to Aspirin and those randomised to placebo is not equal.

Primary objective: To compare DFS between the group randomised to Aspirin with the group randomised to placebo control in subjects with Dukes C or high risk Dukes B colorectal cancer.

Secondary objectives

1. To compare the DFS between the group randomised to Aspirin with the group randomised to placebo control in subjects with high risk Dukes B and Dukes C colon cancer.
2. To compare the overall survival (OS) between the group randomised to Aspirin with the group randomised to placebo control in subjects with Dukes C or high risk Dukes B colorectal cancer.

Exploratory objectives

1. To compare the DFS and OS between the group randomised to Aspirin with the group randomised to placebo control in subjects with Dukes C or high risk Dukes B colorectal within the following subgroups:
 - a. Baseline variables
 - i. Country.

Countries with small sample size (less than 25) will be pooled under 'Others' or with countries with similar ethnic population.

- ii. Resected high risk Dukes B colon cancer, Dukes C colon cancer, colon cancer and rectal cancer.
- iii. Exposed to Oxaliplatin, not exposed to Oxaliplatin.
- iv. Ethnicity (East Asian, South Asian, Caucasian and Others).
- v. Type of surgery (laparoscopic surgery, open surgery).
- vi. Chemotherapy duration (<3 months, 3-6 months, >6 months).
- vii. Age group (<70, ≥70).

b. Translational variables

- i. Compliant subjects, non-compliant subjects.

Compliant subject is defined as an individual who is on the study drug for at least 70% of days in first year from randomisation or up to treatment discontinuation or recurrence, whichever is earlier.

- ii. Duration of exposure to study drug (<1 year, 1-2 years, >2 years).

The duration of exposure to study drug during the treatment period is defined as the number of days from the first dose to the last dose excluding days of interruptions, i.e. "duration of exposure" = "last dosing date" – "first dosing date" – "days off medication" + "1 day".

- iii. PIK3CA mutations (mutant PIK3CA, wild-type PIK3CA)

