4.2 Analysis Populations

All efficacy analyses will be carried out on modified intention-to-treat (mITT) basis, i.e., all subjects who signed the informed consent form for the study enrolment and commenced study treatment after the randomisation are to be analysed as randomised.

As part of sensitivity analysis, efficacy analysis on per-protocol basis will also be performed. Per-protocol analysis consists of subjects included in the mITT population after excluding those with major protocol deviation and those who were compliant <70% of the days in the first year from randomisation. Compliance has been defined in section 2.

Subjects included in safety data analysis are those who received at least one dose of the study treatment drug. These subjects will be grouped and analysed as actually treated.

The number of subjects screened, randomised to the study treatment, completing each subsequent study period including up to 3-year treatment and 5-year follow-up will be summarised in a CONSORT flow chart.

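### AE and SAE recording stops 30 days after final drug cessation, yet the SAP compares arms only by crude ever-reported percentages and counts; unequal stopping would under-count the arm with the shorter window

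*SAP*

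**What the plan says.** **Recording window.** Protocol 13.2 states that "AEs and SAEs will be recorded from the time of entry into the study until 30 days after the full completion of study treatment". Patients who come off drug early have the same 30-day limit, counted from their final stop. Planned treatment is three years (Protocol 9.1: "The patient will be treated with the same study drug for 3 years"), so the longest window is about 3.08 years. Protocol 11.3 keeps early stoppers on three-monthly visits, but its AE item refers back to 13.2. The visit schedule in Appendix 3 agrees: AE/SAE is marked only in the two on-schedule columns for months 3 to 36. The columns for follow-up after recurrence and after early discontinuation carry no AE/SAE mark, although death, medical events and recurrence are marked there.

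**What closes the window.** Protocol 9.3: "Study drug will be stopped immediately if there is disease recurrence confirmed by CT, histology or cytology". Section 9.3 also allows stopping for safety, and the table in 9.2 lists permanent stops for some events.

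**Summary measure.** SAP 4.7 presents "Number and percentage of subjects who ever reported adverse event (AE) and serious adverse event (SAE" by treatment group, with numbers of events. SAP 4.2 sets the denominator: "Subjects included in safety data analysis are those who received at least one dose of the study treatment drug". The shell of Table 9 ("Subjects ever experienced any AE, n") and the shells of Tables 10 to 13 follow the same layout. No time-to-first-event analysis or person-time rate is planned.

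**Exposure.** SAP 2 measures exposure between the first and last dosing dates and takes off any interruptions. SAP 4.4 and Table 2 describe this by arm for the mITT and per-protocol sets. It is not linked to the AE tables.

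**The concern.** Time under AE observation is decided after randomisation, by events that treatment can influence. More intolerance on aspirin would shorten the aspirin window; fewer recurrences on aspirin would lengthen it. A crude percentage of all treated patients ignores this, so the two columns of Tables 9-13 may describe different lengths of follow-up.

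Patients have finished resection and standard therapy and are asked to take drug for three years, so tolerability is part of the benefit-risk judgement. Protocol 13.1 expects the commonest aspirin AEs to be gastrointestinal. In SAP 4.7 the separately followed GI event is bleeding that needs transfusion. Lesser GI bleeding, ulcer and gastritis therefore appear only in the AE/SAE outputs, where the 30-day limit applies.

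**Working it through.** The documents state no AE rate, stopping rate or safety power, so there is no figure to reproduce. The check measures how far the crude percentage moves when the true AE rate is identical in both arms.

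**Inputs from the documents.** Treatment 3 years; tail w = 30/365.25 = 0.082 years; pooled DFS 79% at 5 years (Protocol 12.1). If exponential, recurrence or death stops drug at −ln(0.79)/5 = 0.047 per year.

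**Assumptions.** Constant first-AE hazard λ; other stopping at 5% per year on placebo and 10% or 20% on aspirin; recurrence or death equal in the two arms; stopping independent of AEs.

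**Formulas**, with d the total stopping hazard:

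- Mean window = (1 − e^(−3d))/d + w
- Crude proportion = 1 − e^(−λw) × [ d/(d+λ) × (1 − e^(−3(d+λ))) + e^(−3(d+λ)) ]

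**Results at λ = 0.10 per year (e^(−λw) = 0.9918)**

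| Arm | d | Mean window (y) | Crude proportion | Ratio to placebo |
|---|---|---|---|---|
| Placebo, 5%/y | 0.097 | 2.68 | 1 − 0.9918 × (0.4928 × 0.4465 + 0.5535) = 23.3% | – |
| Aspirin, 10%/y | 0.147 | 2.51 | 1 − 0.9918 × (0.5954 × 0.5236 + 0.4764) = 21.8% | 0.94 |
| Aspirin, 20%/y | 0.247 | 2.20 | 1 − 0.9918 × (0.7119 × 0.6471 + 0.3529) = 19.3% | 0.83 |

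With aspirin stopping at 8% per year the ratio is 0.96. For λ from 0.05 to 0.60 per year, the ratio is 0.94 to 0.95 at 10% and 0.83 to 0.87 at 20%.

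**Opposite direction.** Suppose the design hazard ratio of 0.72 is true and other stopping is 5% per year in both arms. Recurrence or death then stops drug at 0.047 × 2/1.72 = 0.055 per year on placebo and 0.72 × 0.055 = 0.039 on aspirin. The crude figures are 23.5% on aspirin and 23.0% on placebo, ratio 1.02, so aspirin now looks slightly worse.

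**Early-onset AEs, and whether patient-years would cure the problem.** Take an identical hazard in both arms of 0.4 per year for six months, then 0.05. Person-time to first event or end of window is the integral of P(window > u) × P(no AE by u).

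| Aspirin v placebo stopping | Crude % | Crude ratio | First events per 100 patient-years | Rate ratio |
|---|---|---|---|---|
| 10% v 5%/y | 25.5 v 26.3 | 0.97 | 25.5/2.00 = 12.7 v 26.3/2.13 = 12.3 | 1.035 |
| 20% v 5%/y | 24.1 v 26.3 | 0.915 | 24.1/1.77 = 13.6 v 26.3/2.13 = 12.3 | 1.106 |

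A single patient-year rate errs the other way, by a similar or larger amount.

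**Cumulative incidence.** If stopping is not informative for later AEs, censoring at the end of the window leaves the same target in both arms. Leaving death aside, three-year incidence is 1 − e^(−0.30) = 25.9% at λ = 0.10. In the early-onset case it is 1 − e^(−(0.4×0.5 + 0.05×2.5)) = 27.7%. This holds whatever the two stopping rates are.

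**The case against.** The case for leaving the plan alone has real weight.

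- **No test rests on these tables.** SAP 4.7 tests only the medical events. AE/SAE figures are descriptive, and crude incidence with exposure reported separately is common practice. This stands, and it limits the point.
- **The gravest harms are followed after drug stop.** Myocardial infarction, strokes, new cancers, transfused GI bleeding and major nervous system bleeding are counted throughout the study, and Protocol 13.3 covers deaths beyond 30 days. This stands.
- **Most gastric rows in Protocol 9.2 reduce the dose or interrupt drug with possible rechallenge.** The 30-day clock starts at final cessation, so these do not close the window. A patient stopped for an AE also already counts under any AE. Both stand. What distortion there is falls mainly on SAEs, other SOC/PT rows and event counts.
- **Large stopping differences are unsupported.** The only excess-harm figure for major bleeding is 0.13% per year (Protocol 7.8), about 0.4 points over three years. It does not cover minor intolerance. If 1 to 3 more points of aspirin patients stop at one year, against 10% to 20% on placebo, the ratio of mean windows is 0.99 to 0.98: for example (0.11 × 1.082 + 0.89 × 3.082)/(0.10 × 1.082 + 0.90 × 3.082) = 0.99. The effect may well be small.
- **Table 2 already shows exposure, and Table 1 the reasons for stopping.** This is only a partial answer. Table 2 subtracts days off drug, which still lie inside the AE window, and it groups patients as randomised, whereas the AE tables group them as treated. A gross imbalance would show, but readers could not correct for it.

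A reader might infer that the plan makes aspirin look safer, or hides its harm. The documents do not support that: they give no stopping rates, and the two routes to stopping push in opposite directions.

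**Conclusion.** The point holds as a conditional weakness of the descriptive AE/SAE outputs (SAP 4.7, Tables 9-13). The recording window depends on final drug cessation, treatment can change that, and the planned measure does not allow for it. If final stopping differs by arm, the arm with the shorter window is under-counted.

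Neither direction nor size can be established from the documents. The ratios of 0.94 and 0.83 rest on assumed stopping rates, a constant AE rate equal in both arms and equal recurrence. They move towards 1 when stopping differs little or AEs occur early, and pass slightly above 1 if aspirin mainly delays recurrence. The Table 14 medical events, deaths and the efficacy analyses are untouched. The addition is worth making because it is cheap; it is not a fault in the primary analysis.

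**What to change.** Keep the crude tables as descriptive. In SAP 4.7, for the safety population, add:

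1. Cumulative incidence of first AE, first SAE and first GI or bleeding event by arm. Count from first dose to last dose + 30 days, censor at the end of that window and treat death as a competing event. Give estimates at 1, 2 and 3 years and the between-arm difference with 95% CI. Fix the MedDRA terms for the GI/bleeding group before unblinding.
2. Mean and median AE-observation time by arm, printed above Tables 9-13, without subtracting temporary interruptions.
3. Patient-year rates, if wanted, only as a supplement and split by period (for example 0-6 months and later), because a single rate assumes a constant hazard.

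**Cost.** SAP wording and a few extra outputs. First and last dose dates are already needed for the SAP exposure formula. Onset dates are already planned for the SAE listing, and Protocol 13.1 requires the duration of every AE to be evaluated, so no new data collection should be needed. The price is an assumption that stopping is not informative for later AEs, which should be stated beside the results. Events between study entry and first dose fall outside the added analysis and remain in the crude tables.
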